10.7 Interim Analyses

10.7.1 Efficacy Interim Analysis

An IA for testing the primary efficacy hypothesis will be conducted upon accrual of a total of 15 CMVi endpoint cases in the combined V160 3-dose and placebo regimens. Possible outcomes of this IA and consequent study pathways are as described below and shown in schematic form in [Figure 2](#).

1. ≥7 of 15 CMVi cases observed in the V160 3-dose arm
 - Study fails to demonstrate the primary efficacy hypothesis at the IA and has no chance of successfully demonstrating the primary efficacy hypothesis in a final analysis when a total of 24 CMVi cases are accrued in the combined V160 3-dose regimen and placebo groups.
 - eDMC may recommend the study to be terminated for futility.
2. (4, 5, or 6) of 15 CMVi cases observed in the V160 3-dose arm.
 - Result of testing of the primary efficacy hypothesis is inconclusive.
 - Study fails to demonstrate the primary efficacy hypothesis at the IA but still has a chance of demonstrating the primary efficacy hypothesis in a final analysis when a

total of 24 CMVi cases are accrued in the combined V160 3-dose regimen and placebo groups.

- Study (which is still blinded) will continue until a total of 24 CMVi cases are accrued in the combined V160 3-dose regimen and placebo groups, at which time, the final testing of the primary efficacy hypothesis will be conducted.
3. ≤ 3 of 15 CMVi cases observed in the V160 3-dose arm
- Study successfully demonstrates the primary efficacy hypothesis.
 - The appropriate timing for the testing the secondary efficacy hypothesis is evaluated (see Section 10.6.1).

[figure not shown]

Figure 2 Plan for Testing the Primary and Secondary Efficacy Hypotheses

10.7.2 Safety Interim Analysis

At the time of IA for efficacy, the eDMC will also conduct a review of the cumulative study safety data recorded in the study database upon which the 15 CMVi cases was counted and confirmed to have been accumulated. No hypothesis relating to safety will be tested. Summaries of safety parameters identified in Section 10.6.3 Statistical Methods for Safety Analyses, will be prepared for review by the eDMC.

10.8 Multiplicity

The overall 1-sided Type 1 error in testing the efficacy hypotheses is controlled to not exceed 2.5% based on gatekeeping procedure.

The primary efficacy hypothesis will be tested at an overall (over the IA and final analysis) 1-sided Type 1 error $<2.5\%$, as discussed in Section 10.9.1.1. The secondary efficacy hypothesis will be tested at 1-sided Type 1 error $\leq 2.5\%$ only if the primary efficacy hypothesis is successfully demonstrated, as discussed in Section 10.9.1.2. The primary efficacy hypothesis is a reasonable gatekeeper to the secondary efficacy hypothesis because if a V160 3-dose regimen with last dose at Month 6 is not efficacious, then a V160 2-dose regimen with last dose also at Month 6 is highly unlikely to be efficacious.

10.9 Sample Size and Power Calculations

10.9.1 Sample Size and Power for Efficacy Analyses

10.9.1.1 Sample Size and Power for Testing the Primary Efficacy Hypothesis

The power corresponding to the decision rule that will be implemented in testing the primary efficacy hypothesis is based on a fixed-event design. For testing the primary efficacy hypothesis, participants will be followed until 15 total CMVi cases in the combined V160 3-dose and placebo regimens have been accumulated, at which point, an IA will be conducted. If the testing of the primary efficacy hypothesis is inconclusive at the IA, follow-up will continue until 24 total CMVi cases have been observed in the combined V160 3-dose and placebo regimens. The decision rules to be implemented that will determine success or failure to demonstrate the primary efficacy hypothesis are as shown in [Figure 2](#) in Section 10.7 and in [Table 6](#). Corresponding to these decision rules, the study has $>90\%$ power to demonstrate that the efficacy of a V160 3-dose regimen compared to placebo to prevent CMVi is $>0\%$ if the underlying vaccine efficacy is $\geq 80\%$ at an overall one-sided Type 1 error equal to 2.3%. The operating characteristics of the decision rules with one IA and a final analysis if necessary are evaluated by a 5 million-replication simulation using SAS v9.4. In the simulation conducted, the underlying probability distribution of accumulation of CMVi cases in the V160 3-dose regimen conditional on the total cases in the combined V160 and placebo regimens is based on an exact method under a large sample Poisson distribution assumption proposed by Chan and Bohidar (1998) [Chan, I. S. F. and Bohidar, N. R. 1998].

This study will randomize 700 participants into the V160 3-dose regimen and 700 into the placebo regimen. The 15 total CMVi cases in the combined V160 3-dose and placebo regimens are projected to be accumulated in ≈ 18 to 19 months under the following assumptions: 1) all 1,400 participants are enrolled within 18 months; 2) incidence of CMVi in the placebo group is 2% per year; 3) VE=85%, so that the incidence of CMVi in the V160 arm is 0.3% per year; 4) loss-to-follow-up is $\approx 5\%$ to 10% per year; and 5) participants ineligible for the PPE analysis is $\approx 2\%$ to 5% of participants randomized. Under the same assumptions, the total of 24 CMVi cases in the combined V160 3-dose and placebo regimens is projected to be accumulated in ≈ 3 years.

It is possible that at the time when CMVi cases are counted to determine whether a total of 15 cases have been accrued, the actual CMVi cases accumulated will already be greater than 15. In such an eventuality, the IA will be conducted based on the actual number of cases accrued (eg, 16, or 17, or some other count). The operating characteristics shown in [Table 6](#) will be recalculated, which will involve recalculating the total number of events needed at the final analysis in order to maintain an overall (ie, cumulative over the IA and final analysis) 1-sided Type 1 error $\leq 2.5\%$ and overall power $> 90\%$ when the underlying vaccine efficacy is $\geq 80\%$.

Table 6 Decision Rule and Corresponding Type 1 Error and Power for Testing the Primary Efficacy Hypothesis of VE >0% Against CMVi (3-Dose Regimen vs. Placebo)

| Analysis Time Point | Total Cases to Accrue | Stop for Futility (Vacc Cases) | Case Split for Success (Vacc:Pbo) | VE (95% CI) | Cumulative Type I Error | True Vaccine Efficacy | | | | | |
|---------------------|-----------------------|--------------------------------|-----------------------------------|-------------------|-------------------------|-----------------------|-------|-------|-------|-------|-------|
| | | | | | | 70% | 75% | 80% | 85% | 90% | 95% |
| | | | | | | Cumulative Power | | | | | |
| IA | 15 | ≥7 | ≤3 : ≥12 | 75.0 (7.4, 95.5) | 1.8% | 53.2% | 64.8% | 76.8% | 87.8% | 95.9% | 99.5% |
| Final [†] | 24 | ≥7 | ≤6 : ≥18 | 66.7 (12.3, 89.2) | 2.3% | 73.0% | 83.7% | 92.3% | 97.5% | 99.6% | 100% |

[†] Type I error and power shown are cumulative over the IA and final analysis.
 CI = Confidence interval; IA = Interim analysis; VE = Vaccine efficacy.

10.9.1.2 Sample Size and Power for Testing the Secondary Efficacy Hypothesis

The power corresponding to the decision rule that will be implemented in testing the secondary efficacy hypothesis is based on a fixed-event design. The secondary efficacy hypothesis will be tested when a total of ≥ 15 CMVi cases in the combined V160 2-dose and placebo arms have been observed (see [Figure 2](#) in Section 10.7). When the secondary efficacy hypothesis is tested based on a total of ≥ 15 CMVi cases, the study has $>85\%$ power to demonstrate that the efficacy of a V160 2-dose regimen compared to placebo to prevent CMVi is $>0\%$ if the underlying vaccine efficacy is $\geq 85\%$ at an overall one-sided Type 1 error $\leq 2.5\%$ (see [Table 7](#)). The calculations are based on an exact method under a large sample Poisson distribution assumption proposed by Chan and Bohidar (1998) [Chan, I. S. F. and Bohidar, N. R. 1998] and carried out using the R software.

This study will randomize 700 participants into the V160 2-dose regimen and 700 into the placebo regimen. Under the same assumptions governing the accumulation of CMVi cases in the V160 3-dose and placebo arms, a total of 15 CMVi cases in the combined V160 2-dose and placebo arms are projected to be accumulated in ≈ 18 to 19 months; and a total of 24 in ≈ 3 years.

Table 7 Decision Rule and Corresponding Type 1 Error and Power for Testing the Secondary Efficacy Hypothesis of VE >0% Against CMVi (2-Dose Regimen vs. Placebo)

| Analysis Time Point | Total Cases Accrued | Case Split for Success (Vacc:Pbo) | VE (95% CI) | Type I Error | True Vaccine Efficacy | | | | | |
|---------------------|---------------------|-----------------------------------|-------------------|--------------|-----------------------|-------|-------|-------|-------|-------|
| | | | | | 70% | 75% | 80% | 85% | 90% | 95% |
| | | | | | Power | | | | | |
| Final | 15 | ≤3 : ≥12 | 75.0 (7.4, 95.5) | 1.8% | 53.2% | 64.8% | 76.8% | 87.8% | 95.9% | 99.5% |
| | 16 | ≤3 : ≥13 | 76.9 (16.0, 95.8) | 1.1% | 47.7% | 59.8% | 72.9% | 85.4% | 94.9% | 99.4% |
| | 17 | ≤4 : ≥13 | 79.2 (0.4, 92.7) | 2.5% | 64.7% | 75.8% | 86.0% | 93.9% | 98.5% | 99.9% |
| | 18 | ≤4 : ≥14 | 71.4 (9.0, 93.2) | 1.5% | 59.6% | 71.6% | 83.2% | 92.5% | 98.1% | 99.9% |
| | 19 | ≤4 : ≥15 | 73.3 (16.3, 93.6) | 1.0% | 54.5% | 67.3% | 80.1% | 90.9% | 97.6% | 99.8% |
| | 20 | ≤5 : ≥15 | 66.7 (3.5, 90.5) | 2.1% | 69.3% | 80.4% | 89.8% | 96.2% | 99.3% | 100% |
| | 21 | ≤5 : ≥16 | 68.8 (10.7, 91.0) | 1.3% | 64.8% | 76.9% | 87.7% | 95.3% | 99.1% | 100% |
| | 22 | ≤5 : ≥17 | 70.6 (16.9, 91.5) | 0.8% | 60.2% | 73.3% | 85.3% | 94.2% | 98.8% | 100% |
| | 23 | ≤6 : ≥17 | 64.7 (6.2, 88.6) | 1.7% | 73.2% | 84.0% | 92.5% | 97.7% | 99.7% | 100% |
| | 24 | ≤6 : ≥18 | 66.7 (12.3, 89.2) | 1.1% | 69.1% | 81.1% | 90.9% | 97.1% | 99.6% | 100% |

CI = Confidence interval; VE = Vaccine efficacy.

10.9.2 Sample Size and Power for Safety Analyses

Testing of hypotheses relating to safety will not be conducted in this study. Thus, power and Type 1 error considerations relating to safety analyses are not applicable in this study.

The probability of observing a specific AE in specific treatment arms of this study depends on the number of vaccinated participants with safety follow-up and the underlying incidence of that specific AE in the study population. In each treatment arm, assuming that all 700 participants randomized into the study will have safety follow-up, then there is a >99% chance of observing at least one specific AE if the incidence of that AE is at least 1 in every 150 participants; >90% chance if the incidence is at least 1 in every 300 participants. If no vaccine-related SAEs are observed among the 700 participants randomized in a specific V160 treatment arm, this study will provide 97.5% confidence that the underlying percentage of participants with vaccine-related SAE is $\leq 0.5\%$ (1 in every 200 participants) among V160 vaccinated participants in that V160 arm. This is based on calculation of a 1-sided 97.5% upper confidence limit of a binomial proportion using the exact binomial method of Clopper and Pearson [Clopper, C. J. and Pearson, E. S. 1934] and was done using PASS 2008. For a sample size of 700 per treatment arm, Table 8 provides the critical split of participants with AEs between V160 and placebo arms for which it will be possible to state with 95% confidence that the risk difference (defined as percent in V160 dose regimen group minus percent in placebo) excludes 0%. For a specific AE, given a sample size of 700 per arm, the minimum total number of participants with AEs for which it is possible to state with 95% confidence that the risk difference excludes 0% is 5. As stated in Section 10.6.3, AEs observed in at least 7 participants (representing 1% of N=700 participants per group) in any vaccination group will be categorized as a Tier 2 event. The 95% CIs of the percentage point differences were calculated using the Miettinen and Nurminen method [Miettinen, O. and Nurminen, M. 1985].

Table 8 Critical Counts of Participants with Adverse Events in V160 and Placebo Arms Resulting in the Lower Bound of 95% CI Estimate of Risk Difference to be >0%

| Observed Count of Participants with Adverse Events | | | Risk Difference [†] (V160 – Placebo) | |
|----------------------------------------------------|--------------|-----------------|-----------------------------------------------|---------------------|
| Total | V160 (N=700) | Placebo (N=700) | Percentage Points [‡] | 95% CI [§] |
| 5 | 5 | 0 | 0.7% | (0.1%, 1.7%) |
| 6 | 6 | 0 | 0.8% | (0.3%, 1.8%) |
| 7 | 7 | 0 | 1.0% | (0.4%, 2.0%) |
| 8 | 7 | 1 | 0.9% | (0.1%, 1.9%) |
| 9 | 8 | 1 | 1.0% | (0.2%, 2.1%) |
| 10 | 9 | 1 | 1.1% | (0.3%, 2.3%) |
| 11 | 9 | 2 | 1.0% | (0.1%, 2.2%) |
| 12 | 10 | 2 | 1.1% | (0.2%, 2.4%) |
| 13 | 11 | 2 | 1.3% | (0.4%, 2.5%) |
| 14 | 11 | 3 | 1.1% | (0.1%, 2.4%) |
| 15 | 12 | 3 | 1.3% | (0.3%, 2.6%) |
| 16 | 13 | 3 | 1.4% | (0.4%, 2.8%) |
| 17 | 13 | 4 | 1.3% | (0.2%, 2.6%) |
| 18 | 14 | 4 | 1.4% | (0.3%, 2.8%) |

| Observed Count of Participants with Adverse Events | | | Risk Difference [†] (V160 – Placebo) | |
|----------------------------------------------------|--------------|-----------------|-----------------------------------------------|---------------------|
| Total | V160 (N=700) | Placebo (N=700) | Percentage Points [‡] | 95% CI [§] |
| 19 | 15 | 4 | 1.6% | (0.4%, 3.0%) |
| | 14 | 5 | 1.3% | (0.1%, 2.7%) |
| 20 | 15 | 5 | 1.4% | (0.2%, 2.9%) |

[†] Defined as percent of participants in the V160 group with adverse events minus the corresponding percent in the placebo group.
[‡] Calculated as $100\% \times (\text{V160} - \text{Placebo}) \div 700$.
[§] Calculated based on the Miettinen and Nurminen method.
N = Number of participants randomized.
CI = Confidence interval

10.10 Subgroup Analyses and Effect of Baseline Factors

To determine whether VE is consistent across various subgroups associated with specific baseline participant characteristics, the estimate of the VE (with a nominal 95% CI) for the primary efficacy endpoint (comparing 3-dose regimen versus placebo) and for the secondary efficacy endpoint (comparing 2-dose regimen versus placebo) will be estimated and plotted within each subgroup. Subgroup assessments of VE will be conducted for the following baseline participant characteristics:

- Age category (≤ 21 vs. > 21 years)
- Race (white, non-white)
- Region (US, Ex-US)

For each of the primary and secondary efficacy endpoints, a Forest plot will be produced, which provides the estimated point and 95% CI estimates of VE across the subgroups associated with specific baseline participant characteristics listed above. The consistency of VE across subgroups will be assessed descriptively based on these Forest plots.

10.11 Compliance

10.11.1 Adherence to Scheduled Vaccinations

Compliance to scheduled vaccinations in this study is defined as receipt of all 3 vaccinations of either V160 or placebo. To summarize compliance, the numbers of participants who receive each vaccination will be tabulated. For each of vaccination visits 2 and 3, histograms of the time (in days) of administration of the vaccine or placebo relative to the target vaccination visit will be provided.

10.11.2 Adherence to Scheduled Self-Collection of Urine and Saliva Samples

Accurate and reliable ascertainment of the primary and secondary efficacy endpoints (ie, incidence of CMVi) will depend on compliance of study participants to the self-collection of urine and saliva samples based on the schedule indicated in Section 2. Thus, compliance of

study participants to the self-collection of urine and saliva samples will be assessed as follows.

On a participant-level (say the i -th participant among the $N=2100$ study participants), percent compliance (denoted by P_i) of a study participant to the self-collection of urine and/or saliva samples will be calculated as:

$$P_i = \frac{n_i}{M_i} \times 100\%$$

where

n_i = number of visits for which either a urine or saliva sample was received from the study participant;

M_i = total number of study visits throughout the study for which a urine or saliva sample is expected to be received from the study participant. This number will vary based on the time when the study participant enters the study and the time when the study ends.

For each of the V160 3-dose, V160 2-dose, and placebo arms, point and 95% CI estimates of the geometric mean of the participant-level percent compliance P_i will be calculated to summarize the vaccination group-level compliance of study participants to the self-collection of urine and saliva samples.

This assessment of compliance of study participants to the self-collection of urine and saliva samples will be conducted in both the PPE and FAS analysis populations.

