9.2.1.1.2 CMVi Case Detection

At Visit 2 (Day 1), participants will be trained on proper saliva and urine sample collection procedures using the self-collection kits provided. The first set of samples will be collected on site by the participant. All other samples will be collected monthly, from Month 1 to approximately Month 36, by the participant outside of the study site (eg. at home or place of employment) or at scheduled site visits (when applicable), as indicated in the SoA.

In addition to on-site training, instructional materials will be provided to the participant to use as a reference. Participants will contact the site with any questions or concerns they have regarding the self-collection process. Reminder contacts will be made monthly to the participants, to prompt their collection of samples. Receipt of the samples will be tracked in real-time in order to provide feedback to the site. The site will contact and re-train participants who are missing samples or submitting samples which are unacceptable for testing. Detailed instructions will be provided to the site for monitoring self-collection and sample handling.

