10.4.1 Efficacy Endpoints

The efficacy endpoint that will be used to evaluate VE and test the primary and secondary efficacy hypotheses is the number of participants with primary CMVi, described in Section 4 and Section 5.4.1.

CMVi is defined as detection of CMV DNA by PCR in urine or saliva samples.

As stated in Section 4, in the evaluation of the primary and secondary efficacy hypotheses, cases of CMVi will be counted starting after the last dose of the assigned vaccination regimen. As stated in Section 10.5.1, the primary and secondary efficacy hypothesis will be evaluated on the PPE population, where eligibility includes being PCR negative post Day 1 through Month 7. Thus, CMVi cases that will be included in the PPE testing of the primary and secondary efficacy hypothesis are those that occurred after Month 7.

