10.5 Analysis Populations

10.5.1 Efficacy Analysis Populations

Per Protocol Efficacy (PPE)

The PPE population will serve as the primary population for the evaluation of VE and for testing the primary and secondary efficacy hypotheses. To be eligible for inclusion in the PPE population, study participants must satisfy the following criteria:

- CMV seronegative at Day 1 and CMV negative by PCR for non-vaccine strain virus from post Day 1 through Month 7
- Have received all 3 injections/vaccinations within the vaccination visit window specified in the SoA (Section 2)
- At any time from Day 1 through Month 7, did not have events, deviations from protocol, or engaged in activities that are deemed by the study Clinical Director to potentially interfere with the evaluation of efficacy or immune response to injections of V160.

Participants whose CMV status by PCR post Day 1 through Month 7 is not evaluable will be ineligible for inclusion in the PPE population. The categories of events, deviations from protocol, or activities that are deemed by the study Clinical Director to potentially interfere with the evaluation of efficacy or immune response to injections of V160 will be identified and documented in a memo to study file prior to the time of the IA for efficacy assessment.

Full Analysis Set (FAS)

The FAS will serve as a supportive analysis population for the evaluation of VE. The FAS population consists of all randomized participants who received at least 1 dose of the correct clinical material corresponding to the treatment regimen the participants were randomized into.

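### The sampling-compliance figure runs from Day 1 and counts any sample received, so it does not measure compliance in the window where per-protocol CMVi cases count

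*Combined protocol and SAP*

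**What the plan says.** Protocol 10.11.2, repeated in sSAP 3.11.2, gives the reason for the measure: "Accurate and reliable ascertainment of the primary and secondary efficacy endpoints (ie, incidence of CMVi) will depend on compliance of study participants". Each participant's compliance is P_i = n_i/M_i × 100%.

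- The numerator n_i is the "number of visits for which either a urine or saliva sample was received from the study participant". It does not require that the sample could be tested.
- The denominator M_i is the "total number of study visits throughout the study for which a urine or saliva sample is expected to be received from the study participant". On how it differs between women, the text says only: "This number will vary based on the time when the study participant enters the study and the time when the study ends". Dropout is not mentioned.
- Each arm is summarised by "point and 95% CI estimates of the geometric mean of the participant-level percent compliance", in both the PPE population and the FAS.

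Three other places bear on this. Under the Schedule of Activities (2.1, 2.2), collection starts on Day 1 and is monthly to about Month 36. Protocol 10.4.1 states that "CMVi cases that will be included in the PPE testing of the primary and secondary efficacy hypothesis are those that occurred after Month 7". Protocol 10.5.1 adds: "Participants whose CMV status by PCR post Day 1 through Month 7 is not evaluable will be ineligible for inclusion in the PPE population". Protocol 9.2.1.1.2 also foresees participants "submitting samples which are unacceptable for testing", so receipt and testability are different things.

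**The concern.** The measure is introduced as support for endpoint ascertainment, but its window and its unit are not those of the endpoint. For the PPE, the eight collections from Day 1 to Month 7 cannot yield a counted case, yet they enter P_i with the same weight as later ones. A sample that cannot be tested gives no chance of detecting CMV, yet it counts as compliance.

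This is the only planned summary of sampling compliance. Section 5.4.1.1 puts shedding after infection at 6 to 8 weeks or perhaps longer, so runs of missed months can lose infections. Incidence in 10.6.1 is cases over person-years of follow-up, with no stated link to the samples actually tested. Success margins are single cases: with the interim analysis at 17 cases and the final at 26, sSAP Table 3 requires at most 7 vaccine cases. A reader of the study report would want to know whether sampling after Month 7 was adequate and similar between arms. The planned figure answers a different question.

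**Working it through.** The documents give no expected, target or minimum compliance, so there is no figure of the plan's own to reproduce. The check applies the plan's formula.

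**Inputs.** Collections are at Day 1 and then monthly: T + 1 for T months of follow-up (Schedule of Activities), of which 8 fall from Day 1 to Month 7 and T − 7 later. Enrolment takes 18 months in a 3-year study (Synopsis), so T is about 18 to 36. Loss to follow-up is 5% to 10% per year (10.9.1.1). Return rates are not given; those below are assumptions.

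**Share of M_i that cannot yield a PPE case: 8/(T + 1).**
- T = 36: 8/37 = 21.6%
- T = 30: 8/31 = 25.8%
- T = 24: 8/25 = 32.0%
- T = 18: 8/19 = 42.1%

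With uniform entry over 18 months and a cut at Month 36, the number of collections runs over 19 to 36 with equal weight (37 only for a woman entering at time zero). The mean share is (8/18) × (1/19 + 1/20 + … + 1/36) = (8/18) × 0.680 = 30.2%.

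**Dilution of an arm difference.** If early return is the same in both arms, a difference D after Month 7 appears as (1 − share) × D. For D = 10 points this is 10 × (1 − 0.302) = 7.0 on average, 10 × 29/37 = 7.8 at T = 36 and 10 × 11/19 = 5.8 at T = 18. This is on the arithmetic scale.

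**Level.** P − late = share × (early − late), before any dropout:

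| Early | Late | P, T = 36 | Gap | P, T = 18 | Gap |
|---|---|---|---|---|---|
| 95% | 90% | 91.1% | +1.1 | 92.1% | +2.1 |
| 95% | 80% | 83.2% | +3.2 | 86.3% | +6.3 |
| 95% | 70% | 75.4% | +5.4 | 80.5% | +10.5 |
| 95% | 60% | 67.6% | +7.6 | 74.7% | +14.7 |
| 90% | 90% | 90.0% | 0 | 90.0% | 0 |
| 80% | 90% | 87.8% | −2.2 | 85.8% | −4.2 |

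The sign depends entirely on which period has the better return.

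**Dropout and the geometric mean.** If months after dropout stay in M_i, loss alone, taken as (1 − r)^(m/12) at month m, gives an arithmetic mean over 36 months of 92.7% for all points against 91.1% after Month 7 (r = 5%), and 85.8% against 82.7% (r = 10%). The planned geometric mean pulls the other way. A simulation of 100,000 women used T = 36, the Day 1 sample always received and 10% yearly loss. It compared the planned full-period geometric mean with the arithmetic mean after Month 7:
- 90% return throughout: 68.2% against 74.3% (all women), and 78.1% against 79.0% (those still in at Month 7). The planned figure reads low.
- 95% early and 70% late: 58.5% against 57.7%, and 66.3% against 61.5%. It reads high.

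**Received versus valid.** Collections with a valid result cannot outnumber collections received, so counting receipt raises P_i or leaves it unchanged. If 95% of received samples were testable (assumed), 70% received would be 70% × 0.95 = 66.5% valid.

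**The case against.** A reader might infer that the reported figure will be too high. The documents do not support that as a general statement. The period effect needs early return to exceed late return, and no rates are given. Equal rates give no period bias and lower early return reverses it. The planned geometric mean, and an M_i not stated to stop at dropout, can pull the figure down.

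A reader might also picture supervised early months against unsupervised later ones. Under 9.2.1.1.2 only the Day 1 set must be collected on site; all later samples may be taken elsewhere or at scheduled visits. Visits coincide with 4 of the 8 early collections (Day 1, Months 2, 6 and 7) and 5 of the 29 later ones (Months 12, 18, 24, 30 and 36). That, and the PPE requirement on PCR status through Month 7, makes higher early return in the PPE plausible. It does not establish it, since the plan does not say how many samples an evaluable status requires.

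The early samples also matter in their own right. They govern PPE eligibility and the previously uninfected condition, and they contribute to the vaccine-type shedding endpoint. A whole-study figure is therefore legitimate. The measure is also run in the FAS, for which no restriction to cases after Month 7 is stated. During conduct, receipt is tracked in real time, participants are retrained, and beta-globin testing, planned to stop after 6 months, may be reinstated.

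All of this stands. What remains is that none of it produces a reported figure for compliance after Month 7, or for samples with a usable result.

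**Conclusion.** The concern holds as a mismatch between purpose and measure. P_i is justified by endpoint ascertainment but does not measure compliance in the PPE endpoint window. About 30% of M_i on average (22% to 42%) comes from collections that cannot yield a PPE case, assuming uniform entry over 18 months and a 36-month cut. A 10-point arm difference after Month 7 shows as about 7 points, assuming similar early return across arms and an arithmetic mean: diluted, not hidden.

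The direction of the overall figure is open. Only the use of receipt instead of a valid result has a known sign, and its size is unknown because no share of untestable samples is given. Nor does the point imply a biased efficacy estimate: P_i has no threshold and enters no efficacy test, estimate or population. This is an inexpensive improvement to a descriptive output.

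**What to change.** Amend sSAP 3.11.2, and protocol 10.11.2 to match:

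- For the PPE, report by arm the compliance over scheduled collections after Month 7, up to the first non-vaccine CMV-positive sample, withdrawal or the data cut, whichever comes first.
- Define n_i as collections with at least one valid CMV PCR result, and state which laboratory status counts as valid.
- Report Day 1 to Month 7 as a separate figure, because it governs PPE eligibility. Report both periods for the FAS.
- Summarise with an arithmetic mean or the distribution of P_i. The geometric mean should go, because a woman in follow-up who sends nothing usable after Month 7 has P_i = 0, which makes it zero or undefined. In the simulations with dropout left in M_i, roughly 3.5% to 7% of all women, and 0.5% to 1.2% of those still in at Month 7, had P_i = 0 after Month 7.
- Give the number of women with no scheduled collection after Month 7, for whom the later figure is undefined.

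The cost is sSAP wording, extra columns and a possibly lower reported compliance. It uses collection dates and PCR results that the trial generates anyway; the documents do not state how untestable samples are coded in the database, so that needs confirming.
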